6.2 Visit Plan

The study visits included subject visits during hospitalization (Visit 1), during which the subjects were enrolled and randomized for subsequent treatment. All subjects randomized to trial treatment will be part of the safety set and will receive clinical evaluation on days 30, 6, 12, 2 and 3 years after the surgery. Follow-up requires the collection of data required by the protocol, including accompanying medication, recording any adverse events and collecting original documents.

The number of visits and duration of the subject may be treated depending on:

- (a) When patients are included in the study;
- (b) When a clear or possible injury occurs, a decision needs to terminate the study early;
- (C) End the study.

Subject follow-up Program:

- Visit 1 inpatient visit;
- Follow-up for 30 days after Visit 2 surgery;

- Follow-up for 6 months after Visit 3 surgery;
- Follow-up for 12 months after Visit 4 surgery;
- Follow-up for 2 years after Visit 5 surgery;
- Follow-up for 3 years after Visit 6 surgery;

6.3 The Data Collection Plan

The following page is the observation and evaluation time during the study (Table 1)

Note:

1. The vital signs include: body temperature, pulse, breathing, and blood pressure.
2. Blood routine and biochemical activities include: white blood cells, red blood cells, platelet count, hemoglobin, liver function (ALT, AST), renal function (urea nitrogen, creatinine), blood lipid (total cholesterol, LDL cholesterol, high density lipoprotein cholesterol, triglyceride), blood sugar, etc.
3. Myocardial injury markers include: CK, CK-MB, TnT/TnI.

Table 1. Observation and Evaluation Schedule during the Study

Visit:	Visit: # 1			Visit 2:	Visit 3: 3	Visit 4: 4	Visit: 5	Visit 6: 6
Evaluation	Entering the Group	Random:	Discharg e:	30 Days \pm 7 Days	6 months \pm 30 Days	12 months \pm 30 Days	2 Year \pm 30 Days	3 years \pm 30 Days
Sign an informed consent form	✓							
Inclusion and exclusion criteria	✓							
Demographic Data	✓							
Related medical history and surgical history, coronary heart disease risk factors	✓							
vital signs, physical examination, weight, height	✓							
Myocardial injury markers	✓		✓					
12-Guided ECG	✓		✓					
Blood biochemistry and blood routine	✓		✓					

Aditant medication	✓		✓	✓	✓	✓	✓	✓
Coronary angiography	✓					✓		
Ststent implantation		✓						
Adverse events, serious Aevent end point related events	✓	✓	✓	✓	✓	✓	✓	✓
Postoperative antiplatelet therapy			✓	✓	✓	✓	✓	✓

Visit 1: entry (in hospital)

Written informed consent must be obtained only to determine the eligibility of the patient's participation in the study. The researchers should inform the subject that even if the subject agreed to attend the study and signed the informed consent form, cardiac catheterization may not warrant the study. The screening records are used to record information about candidates who do not meet the test selection criteria, including, but not limited to, the screening failure.

The subject was hospitalized for a planned coronary surgery (CAG or PCI). The selected CAG shall register and randomly as soon as possible to determine meeting the entry criteria and before any planned or emergency PCI.

Prior to stenting, the following assessment must be completed to confirm the clinical qualification criteria: demographic (date of birth, gender), relevant medical / surgical history, history of smoking, history of family history of coronary heart disease, targeted physical examination, weight, height, medication, vital signs (heart rate, supine blood pressure), and NYHA classification. Laboratory examination (biochemical and blood routine) and myocardial biomarkers (creponin I, creponin T and creatine kinase), ECG, etc.

All subjects were required to undergo cardiac catheterization to evaluate the angiography inclusion and exclusion criteria. Only subjects who met the clinical and angiography qualification criteria were eligible for the trial.

- Record the antiplatelet and anticoagulant agents.
- Record adverse events and endpoint-related events.

Visit 1: from random post to discharge (in the hospital)

Each subject was assigned a strict sequential registration code by a random number table, subsequently receiving a research intervention.

Random tasks must be completed before patients receive PCI and require whether all inclusion / exclusion criteria are met while evaluating patients

- Compliance and drug use.
- Take a 12-guided ECG at 4 days after surgery or before discharge.
- Record the antiplatelet and anticoagulant agents.
- Record adverse events and endpoint-related events.

Visit 1: discharge (in the hospital)

- Record the antiplatelet and anticoagulant agents.
- Record adverse events and endpoint-related events.

30 Days after Visit2 (Surgery)

All subjects in the group must be evaluated 30 days after stenting. Follow-up assessments can be conducted either by telephone or at the research center.

The following assessment must be completed at 30-day follow.

- Adverse events and endpoint-related events to evaluate and collect the original documents.
- Current antiplatelet drugs. Information on dose changes, interruptions, and cessation of medication must be recorded.
- Laboratory examination that DSMB considers necessary

6 months after Visit3 ()

All subjects in the group must be evaluated within 6 months after stenting.

Follow-up assessments can be conducted either by telephone or at the research center. The following assessment must be completed at 6 months of postoperative follow-up.

- Adverse events and endpoint-related events to evaluate and collect the original documents.
- Current antiplatelet drugs. Information on dose changes, interruptions, and cessation of medication must be recorded.

12 months after Visit4 ()

All subjects in the group must receive an angiography evaluation at 12 months after stenting.

- Photoast Data
- Adverse events and endpoint-related events to evaluate and collect the original documents.
- In addition, the researchers will decide which antiplatelet drugs patients should receive at the end of their research treatment as part of their ongoing clinical treatment, and this transition information will be recorded.
- NYHA cardiac function rating
- Under treatment principles, if the patient did not terminate participation in the study, the 12 months or at the end of the follow-up plan to record the end point or serious adverse events.

2 years after Visit 5()

All subjects in the group must be evaluated 2 years after stenting. Follow-up assessments can be conducted either by telephone or at the research center. The following assessment must be completed at 6 months of postoperative follow-up.

- Adverse events and endpoint-related events to evaluate and collect the original documents.
- Current antiplatelet drugs. Information on dose changes, interruptions, and cessation of medication must be recorded.

Visit 6(, 3 years after surgery)

All subjects in the group must be evaluated 3 years after stenting. Follow-up assessments can be conducted either by telephone or at the research center. The following assessment must be completed at 6 months of postoperative follow-up.

- Adverse events and endpoint-related events to evaluate and collect the original documents.
- Current antiplatelet drugs. Information on dose changes, interruptions, and cessation of medication must be recorded.

Unanticipated follow-up

Additional visits for subject safety, drug dose adjustment and need to be recorded in the case report table.

Lost visit

Patients who do not follow-up by protocol and revoke informed consent will repeatedly attempt to contact and determine their life status, the occurrence of any type of myocardial infarction or stroke. If the subject misses any 2 consecutive follow-up and fails to contact (i. e. 2 phone calls, later approved letters), the subject will be deemed missed.

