Compare IVUS with angiography ographic Guidance PCI
Long-term clinical efficacy of acute STEMI

Appisor: The Second Affiliated Hospital
of Zhejiang University Medical
College

Principal investigator (PI): [name]

Key participants: [name], [name], [name]

Center Laboratory: The Second Affiliated Hospital
of Zhejiang University Medical
College

Version Number: Version 1.0

Version Date: April 15th, 2020

Investigator's signature: _____

Directents

COVERFOR.....	1
DIRECTORY.....	2
SCHEMESUMMARY.....	4
RESEARCH FLOWCHART.....	7
1、 RESEARCH	
BACKGROUND.....	8
2、 RESEARCH	
PURPOSE:.....	8
3、 STUDY	
ENDPOINT:.....	8
3.1MAINENDPOINT	8
3.2SECONDARYENDPOINT	8
4、 RESEARCH AND DESIGN.....	8
5、 SUBJECT SELECT.....	9
5.1INCLUSION CRITERIA	9
5.2 ELIMINATION CRITERIA	9
6、 RESEARCH METHODS.....	10
6.1 TREATMENT ALLOCATION METHOD OF SUBJECTS	10
6.2 VISIT PLAN	10
6.3 THE DATA COLLECTION PLAN.....	11
6.4 DRUG TREATMENT	15
6.5 INTRAVASCULAR ULTRASOUND EXAMINATION	15
7、 DATA MANAGEMENT.....	15
7.1 DATA RECORDS.....	16
8、 ETHICS AND REGULATORY REQUIREMENTS.....	16
8.1 ETHICAL CONSIDERATIONS.....	16

8.2. ETHICS REVIEW.....	16
8.3 INFORMED CONSENT FORM.....	16
8.4 REVISION PLAN.....	17
8.5 SCHEME DEVIATION UNDER EMERGENCY CONDITIONS.....	17
9、RESEARCH MANAGEMENT	
9.1 PROGRAMME COMPLIANCE.....	17
9.2 SCHEME MODIFICATION.....	17
10、DATA	
MANAGEMENT.....	17
10.1 DATA COLLECTION AND PROCESSING.....	17
10.2 DATA QUALITY ASSURANCE.....	17
10.3 RAW DATA MANAGEMENT.....	18
10.4 DEFLECTION AND SYSTEM ERROR CONTROL.....	18
11、STATISTICAL ANALYSIS OF.....	18
11.1 STATISTICAL SOFTWARE.....	18
11.2 STATISTICAL METHODS.....	18
11.3 SAMPLE SIZE CALCULATION.....	19
12、RESULTS RELEASED.....	19

Scheme Summary

Clinical ison of Intravascular Ultrasound (IVUS) Guided and Angiography (angiographie) for PCI Acute ST Section Elevated Myocardial infarction (STEMI)

Research Objective	Comparing the long-term clinical efficacy of IVUS-guided and angiography-guided PCI in patients with acute STEMI
Test device	IVUS (Opticross™ catheter)
Control device	NA
Research and Design	Prospective, randomized, and multi-center observational trials
Number of planned subjects	200 Cases
Planned number of locations	Ten clinical sites
Main endpoint	The primary endpoint was major cardiac adverse events (MACE), defined as cardiac death, recurrent myocardial infarction (MI, q and non-q waves), and target vasascularization (TVR) at 12 months.

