Contrast exclusion criteria	
The AE1. bifurcation lesion does not identify it as a criminal lesion
 
The AE2. criminal lesion is located in the left aorta
 
AE3. diffuse lesions associated with unidentifiable criminal lesions
 
AE4. or stent implantation due to stent thrombosis
 
AE5. may plan CABG bypass surgery within 30 days
 
AE6. patients develop renal failure during dialysis

Statistical Methods	
Major statistical assumptions	The IVUS guidance group may have better results than the angiography guidance, especially in TVR or TLR.
Statistical analysis	
Descriptive statistics (e. g., mean, standard deviation, n, minimum, maximum), or median (95% CI) (continuous variable), or frequency tables (classification variables), are used to summarize their demographic characteristics, clinical history, laboratory examination, and risk factors.
 
We will use Logistic regression to analyze the correlation of plaque morphology with clinical results both 12 and 36 months after STEMI.

Sample parameter size	To support the objectives, the sample size of this test will be at least 200 subjects.
Core Laboratory	Core Laboratory data Analysis

1. Research Background

Intravascular ultrasound (IVUS) has been increasingly used for selective and emergency percutaneous coronary intervention. Recent randomized controlled studies, large-scale registration studies, and meta-analysis have demonstrated significant advantages in reducing mortality, myocardial infarction, and target revascularization compared with separate angiographic-guided angiography.

As shown in previous studies [1-5], fewer clinical results on clinical studies of IVUS guided PCI in acute myocardial infarction (AMI) exist and the results remain controversial. This study will explore the effects of IVUS-guided PCI on clinical outcomes in patients with acute ST-segment elevation myocardial infarction (STEMI).

2. Research Objective

Comparing the long-term clinical efficacy of IVUS and angiography-guided PCI in dealing with acute STEMI.

3. study endpoint

.13. Main endpoint

The primary endpoint was major cardiac adverse events (MACE), defined as cardiac death at 12 months, recurrent myocardial infarction (MI, Q and non-Q waves), and target vascular revascularization (TVR).

.23. Secondary endpoint

The following indicators will be evaluated annually for 3 years.

- MACE(2-3 assessed annually)

- Target lesion blood revascularization (TLR)
- Target lesion failure (TLF)

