11.2 Statistical Methods

Statistical description is given below:

Continuous variables: number of group description examples, number of missing cases, average, median, standard difference, quartile range, minimum, and maximum.

Classification variable: Number of missing cases, number of splitting frequencies, and percentage of the group description.

Statistical tests: All statistical tests are bilateral tests, and P values less than or equal to 0.05 will be considered to be of statistical significance. (Unless specifically specified).

Overview of statistical methods: different analysis methods will be adopted according to the classification of groups and data characteristics, see the statistical analysis plan for details. The main statistical analysis methods include t test, card square test, Fisher accurate probability method, ANOVA, covariance, Logistic regression, CMH card square and rank and test methods to compare the differences among different groups.

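### TVR prompted only by the mandatory 12-month angiogram can count as a primary event, because TVR in the primary MACE is not limited to clinically driven procedures

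*Combined protocol and SAP*

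**What the plan says.** The Scheme Summary lists the primary MACE components as cardiac death, "recurrent myocardial infarction (MI, q and non-q waves), and target vasascularization (TVR) at 12 months". Section 3.1 repeats the endpoint with the time point placed differently: "defined as cardiac death at 12 months, recurrent myocardial infarction (MI, Q and non-Q waves), and target vascular revascularization (TVR". Neither place says what prompts a countable TVR. The secondary lists name TVR and TLR without defining them.

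For Visit 4, section 6.3 says "All subjects in the group must receive an angiography evaluation at 12 months after stenting". Table 1 ticks coronary angiography in the column headed "12 months \pm 30 Days". Adverse and endpoint-related events are evaluated at that same visit, and their source documents are collected.

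Three other provisions bear on the point:
- Section 3.2 says of the secondary endpoints, which include the MACE components singly, "The following indicators will be evaluated annually for 3 years".
- Section 11.2 leaves the methods to another document ("see the statistical analysis plan for details"). Section 7 refers to CRF instructions. Neither is supplied separately.
- Section 12 mentions, in connection with authorship, members of what appears to be an endpoint committee. It gives no classification rule and no masking.

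**The concern.** The stated objective is long-term clinical efficacy, and the Scheme Summary expects the benefit of IVUS to show especially in TVR or TLR. The component without a definition is thus the one expected to carry the result.

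A revascularisation done because a scheduled angiogram showed a narrowing is not in itself a clinical event. It follows from an operator's decision, and the plan describes no masking of that decision. Symptom status need not be recorded before the angiogram, and no rule separates a TVR that follows from it. What is at stake is mainly the meaning of the primary endpoint. Power is secondary, since section 11.3 calls this a pilot without a sample size calculation.

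**Working it through.** **Reading.** The endpoint statements, the Visit 4 text and Table 1, taken together, show that:
1. TVR is a primary component with no qualifier.
2. Every subject has an angiogram at 12 months.
3. Endpoint events are collected at that visit.
4. Nothing in the supplied text excludes or flags a TVR that follows from the angiogram.

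Such a TVR can therefore count.

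**Window.** 365 - 30 = 335 and 365 + 30 = 395, so the angiogram falls between about day 335 and day 395. Under a 12-month limit, the same finding could count in a patient seen at day 340 and not in one seen at day 390. Visit 5 is at 730 ± 30, that is day 700 to 760.

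**Size.** The plan gives no event rate, effect or power, so there is no figure to reproduce. From the documents: 200 subjects at 1:1 (100 per arm), two-sided tests, P ≤ 0.05. Everything else is assumed: clinical MACE p of 12% (control) and 6% (IVUS), a triggered fraction t of patients without a clinical event, and a share f of triggered TVR that is counted.

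Observed rate = p + (1 - p) × t × f

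Prompted share = sum over arms of (1 - p) × t × f, divided by the sum of observed rates

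Example, t = 10% in both arms, f = 1:
- Control: 0.12 + 0.88 × 0.10 = 20.8%
- IVUS: 0.06 + 0.94 × 0.10 = 15.4%
- Expected events: 20.8 + 15.4 = 36.2, of which 8.8 + 9.4 = 18.2 are prompted
- Share: 18.2 / 36.2 = 50%

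| Scenario | t, control / IVUS | MACE, control vs IVUS (f = 1) | RR (f = 1) | Prompted share, f = 1 | Prompted share, f = 0.5 |
|---|---|---|---|---|---|
| (a) equal | 1% / 1% | 12.9% vs 6.9% | 0.54 | 9% | 5% |
| (a) equal | 10% / 10% | 20.8% vs 15.4% | 0.74 | 50% | 34% |
| (b) IVUS half | 1% / 0.5% | 12.9% vs 6.5% | 0.50 | 7% | 4% |
| (b) IVUS half | 10% / 5% | 20.8% vs 10.7% | 0.51 | 43% | 27% |
| (c) IVUS double | 0.5% / 1% | 12.4% vs 6.9% | 0.56 | 7% | 4% |
| (c) IVUS double | 5% / 10% | 16.4% vs 15.4% | 0.94 | 43% | 28% |

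Without triggering the RR is 0.50, with 18 expected events. The f = 0.5 column stands for half of the prompted procedures falling after day 365.

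**Power**, by exact binomial enumeration of the uncorrected chi-square test, is 0.324 on the clinical rates alone. With f = 1, the 10% rows give 0.171 in (a), 0.510 in (b) and 0.055 in (c). Power can move either way. In (b) the RR stays near 0.50 only because the assumed triggering ratio equals the assumed clinical RR.

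**Equal clinical MACE**, 10% in both arms: triggering of 8% (control) and 4% (IVUS) gives 10% + 0.9 × 8% = 17.2% and 10% + 0.9 × 4% = 13.6%. The RR is 0.79 and the test rejects in 11.0% of trials. Equal triggering of 8% gives 5.1%.

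**The case against.** **All-TVR is a legitimate endpoint, and the angiogram is scheduled alike in both arms.** Both statements are true. If IVUS reduces angiographic findings, all-TVR MACE has more power, as in scenario (b). That supports reporting it. It does not make an unstated choice a defined one, and the objective is worded in clinical terms.

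**The information may already be there.** Section 6.3 collects source documents for endpoint events, section 8.2 names TVR among the reported events, and section 10.2 requires full source verification. A reader might infer that prompted procedures could never be identified. The documents do not support that, because the reason for a procedure may be recoverable from source. What is missing is a rule that uses it. The secondary TVR and TLR counts show how far TVR drives MACE, but they lack the same qualifier.

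**A time limit exists.** A reader might infer that TVR has none, because section 3.1 attaches the 12 months to cardiac death. The Scheme Summary does give 12 months for the composite. Only the conversion to a day is absent.

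**Bias.** A reader might infer that the design favours IVUS or inflates false positives. The documents fix no direction. Equal triggering dilutes the RR, and unequal triggering can help or hurt. The 11.0% above could reflect operator behaviour or a real angiographic difference.

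**Unseen material.** The separate SAP or the CRF instructions may hold a TVR rule. The point is therefore limited to the supplied text.

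**Conclusion.** The point holds for the supplied text. TVR prompted only by the protocol angiogram can enter the primary endpoint, and near the 12-month boundary the visit date may decide whether it does. This is more than missing detail, because the plan followed as written can count operator-driven, non-clinical events in the component that it expects IVUS to improve.

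The range of about 7% to 50% of primary events (4% to 34% if half fall after day 365) illustrates what is possible. It rests wholly on the assumed 12% versus 6% and on triggering of 1% to 10%, and at the low end the effect is small. Neither the actual size nor the direction can be derived from the documents. The case for a change rests on the endpoint's meaning and does not depend on these figures.

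**What to change.** Keep the angiogram, and change only what is counted and recorded.

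1. In the Scheme Summary and section 3.1, count TVR in primary MACE only when clinically driven: symptoms or objective ischaemia documented before the revascularisation, and not the appearance of the protocol angiogram alone. Apply the same rule to TLR and TVR within TLF and TVF.
2. On the CRF, record symptom and ischaemia status before the Visit 4 angiogram, and the reason for and date of each revascularisation. Have the committee that section 12 alludes to classify them without knowledge of arm.
3. State day 365 as the cut-off for all MACE components in both places. Section 7.1 has adverse events reported until the final visit, and Visit 5 collects endpoint events, so dated events after an early Visit 4 are already obtainable. No extra telephone contact is needed.
4. Report all-TVR MACE as a sensitivity analysis, list angiogram-prompted TVR by arm, and flag any MI complicating an angiogram-prompted procedure.

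If the SAP or CRF instructions already hold a TVR rule, bring it into section 3.1.

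The cost is endpoint wording, a few CRF fields and masked classification. The downside is fewer counted events. In scenario (b) at 10% / 5%, expected events fall from 31.5 to 18 and power from 51% to 32%. In (a) at 10%, events fall from 36.2 to 18 but power rises from 17% to 32%. Two limits remain: an ischaemia test ordered because of the angiogram can still qualify a TVR, and a prompted procedure can pre-empt a later clinically driven one. Both are reasons to keep the all-TVR analysis.

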- Target vascular revascularization (TVR)
- Target blood vessel failure (TVF)
- Myocardial infarction (Q waves and non-Q waves)
- Cardiac death
- Noncardiac death
- All-cause of death (cardiac and noncardiac)
- In-stent thrombosis (ARC classification: determining / possible intrastent thrombosis)

4. Research and Design

This study is a prospective, single-center, randomized controlled trial to be conducted at the Second Affiliated Hospital of Zhejiang University School of Medicine, with plans to recruit 200 STEMI subjects.

Subjects were randomly assigned to 2 treatment groups in a 1: 1 ratio.

5. Subject Selection

Ten centers plan to include 200 male and female patients over 18 to treat subjects according to the Intervention Guidelines of the American Heart Association and the American College of Heart Disease.

The number of subjects recruited each center does not exceed 40% of the total planned enrollment.

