8.2. Ethics Review

Copies of the test protocol, proposed informed consent, other written subjects information, and any suggested advertising materials must be submitted to IEC for written approval. A copy of the IEC written approval of the test protocol and the informed consent form must be obtained before recruiting subjects to enter the study and transport of research products.

Upon all subsequent revisions to the test protocol and all modifications to the informed consent form, the investigator must submit and obtain IEC approval if necessary. The investigator must notify local procedures of deviations or SAE, and intra-stent thrombosis, TVR, MI and death and other SAE reports obtained from the sponsor.

The investigator is responsible for obtaining annual approval and renewal of the TEC throughout the study period. Copies of the investigator report and the IEC renewal documents must be sent to the sponsor.

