10.2 Data quality assurance

Take the necessary control measures to ensure the accuracy and reliability of the data, including reviewing the clinical programs together with the clinical units, and making regular supervisory visits by the sponsor or other designated supervisors. During the clinical site supervision visit, review the accuracy and integrity of the case records and original data, and any errors will be preserved by the clinical unit or supervisor. Beyond this:

- Follow-up rate above 95%
- The Data Administrator challenges the data
- Important indicators for 100% verification
- Monitor 100% data of input system SDV.
- Review the data and give an audit report before the database is locked.

The case record table (Case Report Form, CRF) and the original research data are kept by the researchers, and the data management and statistical unit are responsible for the entry, cleaning, locking library and analysis report of the data.

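### The Lost visit contact in section 6.3 does not ask about target vessel revascularisation or cause of death, so 12-month MACE can stay undetermined in patients reached only that way (minor)

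*Combined protocol and SAP*

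**What the plan says.** The Main endpoint section (section 3) gives MACE as "defined as cardiac death at 12 months, recurrent myocardial infarction (MI, Q and non-Q waves), and target vascular revascularization (TVR"), and the Scheme Summary fixes the assessment at 12 months. The hypothesis in the Scheme Summary is that "The IVUS guidance group may have better results than the angiography guidance, especially in TVR or TLR". The secondary endpoints list cardiac death and noncardiac death separately, and then "All-cause of death (cardiac and noncardiac").

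At scheduled visits, Table 1 in section 6.3 has a row for "Adverse events, serious Aevent end point related events" that is ticked at every time point, and the text for each follow-up visit asks for source documents.

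The Lost visit paragraph at the end of section 6.3 has its own list. It opens with patients who depart from scheduled follow-up and withdraw consent. The English is a translation and does not make clear whether both conditions must hold. For these patients the site is to "repeatedly attempt to contact and determine their life status, the occurrence of any type of myocardial infarction or stroke". A patient is deemed missed under a separate rule: "If the subject misses any 2 consecutive follow-up and fails to contact".

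**The concern.** The list for this contact does not match the primary endpoint. It includes stroke, which is not among the listed primary or secondary endpoints. It leaves out TVR, which is a primary component and one where the sponsor expects a benefit. It asks whether the patient is alive but not why a patient died.

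A site that follows the list exactly could complete the contact and still be unable to say whether the patient had a MACE by 12 months. That patient would then have to be excluded, imputed or counted as event-free. The information is easiest to obtain at the contact itself and may be hard to recover later.

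**Working it through.** The plan states no figure on this point, so there is nothing to reproduce. The check is a comparison of lists, followed by a bound on the size.

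**Step 1: what the listed items settle, up to the date of contact.**

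| Endpoint | On the list? | Patient found alive | Patient found dead |
|---|---|---|---|
| Recurrent MI (primary) | Yes | Settled | Settled |
| Cardiac death (primary) | Only as life status | Settled: absent | Open: cause not asked |
| TVR (primary) | No | Open | Open |
| All-cause death (secondary) | Yes, as life status | Settled: absent | Settled: present |
| Noncardiac death (secondary) | Only as life status | Settled: absent | Open: cause not asked |
| TLR, TLF, TVF, stent thrombosis (secondary) | No | Not settled by the list | Not settled by the list |

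TVR is therefore open in every patient reached only this way. Cause of death is open only in those found dead. If an MI within 12 months is reported, the patient already counts as a MACE and the missing items do not change the composite.

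**Step 2: who is affected.** Patients seen or telephoned at a scheduled visit are not affected, because those visits collect all endpoint events. Patients whom the site cannot reach are not affected either, because a longer list of questions recovers nothing from a contact that fails. What remains is the group reached by this contact and by no scheduled visit. The documents do not give its size.

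**Step 3: size per affected patient.** Inputs:
- r, the 12-month TVR risk. The documents give none, and section 11.3 reports no sample size calculation. Assumed range: 3% to 8%.
- w, the share of the 12 months not covered by an attended visit, between 0 and 1.

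Expected unrecorded TVR events per patient = r × w, with TVR risk spread evenly over the year.
- Upper bound, w = 1: 0.03 × 1 = 0.03 to 0.08 × 1 = 0.08.
- Last seen at 6 months (day 182), w = 183/365 = 0.50: 0.03 × 0.50 = 0.015 to 0.08 × 0.50 = 0.04.
- Seen at 12 months, w = 0: no effect on the primary endpoint.

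The result is proportional to r. If these patients carried twice the assumed risk, the upper bound would be 0.06 to 0.16.

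**The case against.** The strongest reply has four parts.

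First, the opening words point to patients who have withdrawn consent, and a short enquiry is a defensible choice for them. This stands as a limit on the remedy: further questions can go only as far as consent allows. It is not a reason to choose stroke over TVR within the short list.

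Second, other sections may cover patients who have not withdrawn. The 30-day, 6-month, 2-year and 3-year visits may be done by telephone with endpoint events in scope, so a successful call could simply serve as that visit. Section 7.1 requires adverse events to be recorded until the final visit, and section 8.2 refers to "intra-stent thrombosis, TVR, MI and death and other SAE reports obtained from the sponsor". This narrows the gap considerably. None of these passages, however, requires TVR or cause of death to be asked at the Lost visit contact.

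Third, nothing says that the list is exclusive. Staff may ask more, but the paragraph does not require them to.

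Fourth, stroke falls under adverse event recording, so asking about it is not an error. That is accepted. The point is what the list omits.

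A reader might also take the target in section 10.2 ("Follow-up rate above 95" per cent) as a cap on the patients affected and derive a number of missed events from it. The documents do not support this. The rule for deeming a patient missed requires contact to have failed, so those patients are not the ones reached. Nor does the text say whether a patient reached only by this contact counts as followed up.

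**Conclusion.** The point holds as a minor gap in ascertainment. The prescribed list omits one primary component, TVR, and the cause needed to classify a death, for patients reached only by the Lost visit contact. The bound is about 0.03–0.08 unrecorded TVR events per such patient. It rests on an assumed 12-month TVR risk of 3–8% that is not in the documents. The total cannot be given because the number of such patients is not stated.

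Two stronger readings should be avoided. A reader might infer that most of the primary endpoint is lost in these patients. It is not: for a patient found alive, MI and every death endpoint are settled. A reader might also infer a bias between the arms. The paragraph applies equally to both groups, and nothing in the documents indicates that more patients in one arm would be reached only this way.

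**What to change.** Add two items to the Lost visit list in section 6.3, within what each patient's consent allows:
- any repeat revascularisation, whether it involved the target vessel or target lesion, and its date;
- for a patient who has died, the date and cause of death (cardiac or noncardiac), with source documents.

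The cost is a few extra questions and document requests in a contact that is already planned. No new patients, visits or procedures are needed. Patients who have withdrawn may decline to answer, so the change reduces the gap but may not close it.
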